## Design overview

Please ensure all details are in line with the latest version of the protocol.

Trial design, including number of arms		Two-arm Randomised Control Study
Unit of randomisation		Individual CYP
Primary outcome	variable	The primary outcome of interest in this study will be contact with the police, as perpetrators, victims or missing person episodes.
	measure (instrument, scale, source)	Police contact data will be taken from Greater Manchester Police administrative records. Police contact data is a count variable starting at 0. These data will be collected one month before the trial ends. Data will be taken for a period 1 year prior to the recruitment date and 3 months after delivery ends for all CYP.
Secondary outcome(s)	variable(s)	
The secondary outcomes will be the CYP's emotional and behavioural difficulties and self-reported delinquency. Emotional and behavioural difficulties are measured by the following three variables:
 
 
1) Internalizing score
 
2) Externalizing score
 
3) Total difficulties
 
 
Self-reported delinquency is measured by:
 
 
4) Variety of delinquency
 
5) Volume of delinquency
 

	
measure(s) (instrument, scale, source)
	
The first three scores are measured with the Strengths and Difficulties Questionnaire (SDQ). The remaining two scores (4 & 5) are measured with the Self-Reported Delinquency Scale (SRDS).
 
The SDQ and SRDS are completed by CYP at the point of consent, end of the intervention and 6 months after the end of the intervention as a follow-up (for CYP who start the interventions in the first 18 months of the trial).
 
For the SDQ CYP are asked to recall over the past 6 months, a period defined in the measure. For the SRDS, CYP are asked to recall over the past 3 months, this was a period defined for this study, in consultation with Remedi.
 
Scales are 0-20 for the internalizing and externalizing scores and 0-40 for the total difficulties score. Variety of delinquency ranges from 0-19 and volume of delinquency ranges from 0-198 (this excludes the scoring for Question 16, which is different from the other questions).
 
In the pilot study 73% of CYP consented into the interventions completed the initial questionnaires, and between one third and one half completed the end point questionnaires. We would expect these rates to be similar for this efficacy study and so could expect to receive around 257 initial questionnaires and 148 end point questionnaires. Six-month follow up questionnaires were not completed as planned during the pilot study and so we cannot use these completion rates to estimate the expected number of completed questionnaires during the efficacy study. However, we would expect completion rates to be lower than those at the end of the interventions, due to the break in contact with the CYP. As such we estimate between 10-20% of CYP will complete these questionnaires, which would equate to between 35-70 questionnaires. The expected attrition rate will affect the power of the analysis for these secondary outcomes.

Baseline for primary outcome
	
variable
	
The primary outcome of interest is the number of contacts of the CYP with the police, as perpetrators, victims or missing episodes.

	
measure (instrument, scale, source)
	
Police contact data will be taken from Greater Manchester Police administrative records for events 1 year prior to the intervention. Police contact data is a discrete count variable starting at 0.

Baseline for secondary outcome	variable	
The secondary outcomes will be the CYP's emotional and behavioural difficulties and self-reported delinquency.
 
Emotional and behavioural difficulties are measured by the following three variables:
 
 
1) Internalizing score
 
2) Externalizing score
 
3) Total difficulties
 
 
Self-reported delinquency is measured by:
 
 
4) Variety of delinquency
 
5) Volume of delinquency
 

	measure (instrument, scale, source)	
The first three scores are measured with the Strengths and Difficulties Questionnaire (SDQ) and the last two (4 & 5) are measured with the Self-Reported Delinquency Scale (SRDS) questionnaire.
 
The SDQ and SRDS are completed by CYP at the start of the intervention.
 
Scales are 0-20 for the internalizing and externalizing scores and 0-40 for the total difficulties score.
 
Variety of delinquency ranges from 0-19 and volume of delinquency ranges from 0-198 (this excludes the scoring for Question 16, which is different from the other questions).

### Sample size calculations overview

	Protocol	Randomisation
Minimum Detectable Effect Size (MDES)	0.3	0.3
Alpha	0.05	0.05
Power	0.8	0.8

		Protocol	Randomisation
One-sided or two-sided?		Two-sided	Two-sided
Number of participants	intervention	176	176
	control	176	176
	total	352	352

The planned number of the trial participants is 352 CYP in its one year of implementation, 176 in the RM group and 176 in the RC group. The sample size is such that the trial is sufficiently powered to detect a Cohen’s d of at least 0.3 with probability 80%, which is in line with the funder guidelines and the previous literature.

The “simple” randomisation method will be used, which is a robust method against selection and accidental biases. We will use the statistical software package Matlab to implement the randomisation. Automated randomisation will ensure that the process is transparent and reproducible.

The above rest on the assumption that the alpha is equal to 0.05 and that the power is equal to 0.8. The minimum detectable effect size is equal to 0.3 as measured by Cohen’s d.

## Analysis

Descriptive statistics will be presented for the overall sample, as well as for the treatment and control groups separately. The random assignment of cases will be formally tested by comparing means of observable characteristics (such as age, sex, ethnicity among others) between treatment and control groups to check that they are similar across treatment and control groups (see discussion below on imbalance at baseline).

### Primary outcome analysis

The aim of the analysis is to answer the research question: did the Restorative Mentoring intervention (treatment) reduce post-treatment contact with the police compared to the Restorative Choices intervention (control)?

The primary outcome for this study is contact with the police, defined as the number of times the CYP appear in the police data as perpetrators, victims or for missing person episodes. These data will be taken from Greater Manchester Police administrative records.

Contact with the police is a discrete count variable starting at 0. These data will be collected one month before the trial ends, for a period 1 year prior to the recruitment date and for 3 months after completion of the intervention for all CYP.

It should be noted that the primary outcome, which is police contact with the CYP, is susceptible to biases in reporting and recording of crimes. These biases may stem from a number of factors, including characteristics of both the victim and the offender, such as ethnicity and gender. Nevertheless, we anticipate that the RCT design remains robust to these biases, as randomisation into the treatment and control groups is conducted independently of the police's reporting and recording of crimes.

There are two ways of analysing the data, depending on the distribution assumed for the dependent variable, which is total police contacts. As a discrete count random variable, it may be assumed to follow a Poisson or Negative Binomial distribution. However, if the mean of that distribution is far from 0, the Poisson and Negative Binomial distributions may be approximated by the continuous normal distribution. It is not clear a priori which distribution will be the better approximation, and therefore we consider below both scenarios. In any case, we do not expect major differences; the issue of whether a variable should be treated as continuous or discrete has received much attention in the randomized control trial literature and the main finding is that unless the outcome is binary or it is a "time to a first event", information will not be lost when treating a count variable as a continuous one, see, e.g. Herbison et al. (2015).

For the analysis, the headline estimate will be derived from an intention to treat effect (ITT), denoted by  $\beta$  in the regression:

$$g[E(Y_i|T_i)] = \alpha + \beta T_i,$$

where  $Y_i$  is the primary outcome for individual  $i$ , and  $T_i$  is an indicator variable equal to 1 if person  $i$  was assigned to treatment and 0 if person  $i$  was assigned to the control group. The function  $g$  is the link function and is equal to the natural logarithm function if the dependent variable is assumed to be Poisson or Negative Binomial.

Hypothesis testing in the above regression complies with the power predictions of the study. The effect size will be measured by the Incidence Rate Ratio if the data are assumed to be Poisson or Negative Binomial, and by Cohen's  $d$  if they are assumed approximately normal. If the data are Poisson/Negative Binomially distributed, the necessary sample size to detect a "small" effect of at least 1.22, see e.g. Cohen (1992) and Olivier et al. (2017), with  $\alpha=0.05$  and

80% power is 322 CYP equally split between the treatment and control groups. Alternatively, if the data are assumed to be normally distributed, then to detect a “small” effect size of at least 0.3 is 352 CYP. Therefore, a sample of 352 CYP will lead to as sufficiently powered study irrespective of the data distributional assumption.

We will additionally estimate a regression with covariates:

$$g[E(Y_i|T_i, Z_i)] = \alpha + \beta T_i + Z_i' \gamma,$$

where  $Z_i$  is a vector of individual characteristics that are not affected by the intervention (sex, age, ethnicity, district, the number of contacts with the police in the year prior to referral, and referral source). The analysis below depends on the over-arching assumption that the sample of observations are independent to each other. This is reasonable as the sample is only a small subset of the whole population.

The dependent variable here is a count variable and it is highly likely that the lower values will have much higher frequency, in other words it is heavily skewed to the right. This feature of the data suggests that they are best analysed using Poisson regression. Mathematically, the Poisson regression takes the form:

$$Y_i | \lambda_i \sim Poi(\lambda_i)$$

where  $\lambda_i = \alpha + \beta T_i + Z_i' \gamma$ .

An additional assumption that needs to hold for the Poisson regression is that conditionally on the regressors, the mean and variance of  $Y_i$  must be equal to each other. This is called equidispersion. If this assumption does not hold and the variance is greater than the mean, then we must estimate the model using the Negative Binomial regression, which is able to deal with what is called overdispersion.

The Negative Binomial regression works for the same type of data as the Poisson regression, however it also contains an additional term which captures the excess variance, as typically the variance is greater than the mean, when they are not equal. The Negative Binomial distribution is a Poisson-gamma mixture, where a gamma noise variable which has a mean of 1 and a scale parameter of  $\nu$  has been included resulting in the following distribution:

---

 This calculation is based on the average number of police contacts for the control group in the pilot study, which is 1.8. Given that the pilot study participants did not have a full six-month follow-up it is expected that in the efficacy study this average will be much higher. However, the higher the average, the fewer observations are necessary for the power calculations. Therefore, 322 observations is a conservative estimate given that even fewer may be required.

$$P(Y = y_i | \mu_i, a) = \frac{\Gamma(y_i + a^{-1})}{\Gamma(y_i + 1)\Gamma(a^{-1})} \left( \frac{a^{-1}}{a^{-1} + \mu_i} \right)^{a^{-1}} \left( \frac{\mu_i}{a^{-1} + \mu_i} \right)^{y_i}$$

Where  $\mu_i = t_i\mu$  and  $a = 1/v$ . The parameter  $\mu$  may be interpreted as the risk of a new occurrence of the event during a specified exposure period  $t$ .

If the dependent variable can be approximated by the continuous normal distribution, then the regression models above become linear and will be estimated by least squares. In this case, the coefficient  $\beta$  is numerically equal to the difference of means between the control and the treatment group.

Finally, as it is expected that compliance will not be perfect, the analysis will involve estimating a local average treatment effect (LATE), which will provide an estimate of the treatment effect for individuals who engage with the intervention ([Imbens & Angrist \(1994\)](#), [Imbens & Wooldridge \(2009\)](#)). In this case, treatment assignment will be used as an instrument for whether individuals get treated or not (see Compliance section).

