Step 8:	For CYP completing the interventions in the first 18 months of the trial, follow-up SDQ and SRDS questionnaires will be collected, 6 months after the completion of the interventions.
Step 9:	One month before the trial ends, police administrative data are collected from the Police National Computer via GMP.

Table 2: Trial design

Trial design, including number of arms		Two-arm Randomised Controlled Trial
Unit of randomisation		Individual CYP
Stratification variables (if applicable)		N/A
Primary outcome	variable	The primary outcome of interest in this study will be contact with the police, as perpetrators, victims or missing person episodes.

	
measure (instrument, scale, source)
	
Police contact data will be taken from Greater Manchester Police administrative records. Police contact data is a count variable starting at 0. These data will be collected one month before the trial ends. Data will be taken for a period 1 year prior to the recruitment date. Every CYP will have a 3-month follow-up period after completion of the intervention.

Secondary outcome(s)
	
variable(s)
	
The secondary outcomes will be the CYP's emotional and behavioural difficulties and self-reported delinquency. Emotional and behavioural difficulties are measured by the following three variables:
 
 1) Internalizing score 2) Externalizing score 3) Total difficulties 
Self-reported delinquency is measured by:
 
 4) Variety of delinquency 5) Volume of delinquency
	
measure(s) (instrument, scale, source)
	
The first three scores are measured with the Strengths and Difficulties Questionnaire (SDQ). The remaining two scores (4 & 5) are measured with the Self-Reported Delinquency Scale (SRDS).
 
The SDQ and SRDS are completed by CYP at the point of consent, the end of the interventions and 6 months after the end of the interventions as a follow-up (for CYP who start the interventions in the first 18 months of the trial).
 
For the SDQ CYP are asked to recall over the past 6 months, a period defined in the measure. For the SRDS, CYP are asked to recall over the past 3 months, this was a period defined for this study, in consultation with Remedi.
 
In the pilot study 73% of CYP consented into the interventions completed the initial questionnaires,

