		
and between one third and one half completed the end point questionnaires. We would expect these rates to be similar for this efficacy study and so could expect to receive around 257 initial questionnaires and 148 end point questionnaires. Six-month follow up questionnaires were not completed as planned during the pilot study and so we cannot use these completion rates to estimate the expected number of completed questionnaires during the efficacy study. However, we would expect completion rates to be lower than those at the end of the interventions, due to the break in contact with the CYP. As such as estimate between 10-20% of CYP will complete these questionnaires, which would equate to between 35-70 questionnaires.
 
Scales are 0-20 for the internalizing and externalizing scores and 0-40 for the total difficulties score. Variety of delinquency ranges from 0-19 and volume of delinquency ranges from 0-198 (this excludes the scoring for Question 16, which is different from the other questions).

Baseline for primary outcome	variable	The primary outcome of interest is the number of contacts of the CYP with the police, as perpetrators, victims or missing person episodes.
	measure (instrument, scale, source)	Police contact data will be taken from Greater Manchester Police administrative records for events 1 year prior to the intervention. Police contact data is a discrete count variable starting at 0.
Baseline for secondary outcome	variable	
The secondary outcomes will be the CYP's emotional and behavioural difficulties and self-reported delinquency.
 
Emotional and behavioural difficulties are measured by the following three variables:
 
 1) Internalizing score 2) Externalizing score

		
3) Total difficulties
 
Self-reported delinquency is measured by:
 
4) Variety of delinquency
 
5) Volume of delinquency

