The planned number of the trial participants is 352 CYP in its two years of implementation, 176 in the RM group and 176 in the RC group. The sample size is such that the trial is sufficiently powered to detect a Cohen's d of at least 0.3. At the same time, the sample size is in line with the recruitment capacity, funder guidelines and the previous literature, see e.g. O'Connor and Waddell (2015) for a review. The mean effect sizes found in that paper for youth violence interventions range between 0.19-0.4. The calculations are done in Matlab based on Rosner (2011).

Table 3: Sample size calculations

⁷ Community resolution, Youth caution, Youth conditional caution, plus CYP who have been in contact with the police for a violent offence, but no further action has been taken.

		PARAMETER
Minimum Detectable Effect Size (MDES)		0.3
Alpha		0.05
Power		0.8
One-sided or two-sided?		Two-sided
Number of participants	Intervention	176
	Control	176
	Total	352

The above calculations report the sample size for the whole study over a two-year period.

Outcome measures

Primary outcome

The primary outcome of interest is the number of contacts of the CYP with the police, as perpetrators, victims or missing person episodes⁸. This will be measured using police administrative data from Greater Manchester Police (COGNOS system). Data will be taken for a period 1 year prior to the recruitment date and 3 months following the end of the interventions for each CYP. Police contact data is a discrete variable starting at 0.

This is a broad definition and was chosen because the CYP being referred to the RM or RC interventions were expected to have only had limited contact with the police. As a result, relying only on subsequent arrests and proven offending risked minimising their further contact with the police.

Secondary outcomes

The secondary outcomes will be the CYP's emotional and behavioural difficulties (as measured by the Strengths and Difficulties Questionnaire, SDQ) and self-reported delinquency (as measured by the Self-Report Delinquency Scale, SRDS).⁹ CYP will complete these at the point of consent, at the end of the interventions and 6 months

⁸ In cases where a CYP was arrested and rearrested for the same offence, we would create a rule that as this relates to the same offence, this would count as one arrest.

⁹ Full questionnaires for both the SDQ and SRDS are provided at Appendix 2.

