May 2023– June 2025	
Project operation.
 
Key dates:
 
 • CYP consented into the study until 30 November 2024 Delivery ends late February / beginning of March 2025 (for CYP randomised into RM) – closing SRDS / SQDs completed. • Opening, closing and 6-month follow-up SDQs/SRDSs, and Remedi case monitoring data to be gathered on an ongoing basis by Remedi staff throughout the efficacy study. Final data to be shared by 31 March 2025. • CYP (consented up until 31 July 2024) approached to complete 6-month follow-up SDQs/SRDS (ends in May 2025). • GMP data collection undertaken by: 6 June 2025. 
UoB team to gather qualitative data (interviews with staff, referrers, CYP, families, RJ victims) on an ongoing basis throughout the efficacy study, until end May 2025.
	
Remedi
 
UoB

July 2025	Draft final evaluation report	UoB
Sept 2025	Submit final evaluation report	UoB
Oct 2025	Complete support for YEF publication process	UoB

TBC	Data archiving	UoB
-----	----------------	-----

References

Angrist, J. D. (2014). Instrumental Variables (Take 2): Causal Effects in a Heterogeneous World. Delivered as part of MIT 14.387.

Dakof, G. A., Henderson, C. S., Rowe, C. L, Boustani, M., Greenbaum, P., Wang, W., Hawes, S., Linares, C., & Liddle, H. A. (2015). A randomized controlled trial of multidimensional family therapy in juvenile drug court. *Journal of Family Psychology*, 29, 232-241. doi: 10.1037/fam0000053

Darnell, A. J., and Schuler, M. S. (2015). Quasi-Experimental Study of Functional Family Therapy Effectiveness for Juvenile Justice Aftercare in a Racially and Ethnically Diverse Community Sample. *Children and Youth Services Review*, 50, 75-82. doi:10.1016/j.childyouth.2015.01.013.

DuBois, D. L., Holloway, B. E., Valentine, J. C., & Cooper, H. (2002). Effectiveness of mentoring programs for youth: A meta-analytic review. *American Journal of Community Psychology*, 30, 157–197.

Duflo, Esther, Rachel Glennerster, and Michael Kremer. (2008). Using Randomization in Development Economics Research: A Toolkit. T. Schultz and John Strauss, eds., *Handbook of Development Economics*. Vol. 4. Amsterdam and New York: North Holland.

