The RM intervention began operation in Greater Manchester in April 2022. The RM intervention consists of 12 weeks of support comprised of three components, intensive one to one mentoring support for CYP based on 3-4 sessions per week, support for their family to address conflicts/improve communication and relationships, and restorative justice with relevant and appropriate victims of offences or incidents. All CYP in the treatment group will receive the mentoring component but the use of either of the other components will be determined by an initial needs assessment. The CYP in the control group will receive RC, a short mentoring scheme focused on the CYP understanding the causes and effects of their actions. This consists of four sessions usually lasting 1-2 hours (depending on the attention abilities of participants). The sessions will take place over a period dictated by the availability of the CYP - they can all take place during a week or at most over four weeks. Both RC and RM will be delivered by Remedi. The mentors are given extensive training to ensure that CYP are appropriately supported in both programmes and the evaluation teams will regularly

carry out fidelity checks that look at whether the two interventions are being delivered as designed by looking through the number of sessions delivered and random sampling of case worker sessions. This will pick up any hidden bias in how delivery occurs across the two groups.

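### The primary count starts when each young person's own programme ends, so the two arms are observed at different times after randomisation and the headline ratio is unbiased only if the contact rate is constant

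*SAP*

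**What the plan says.** Three places tie the follow-up window to the individual's own completion. The SAP (Primary outcome analysis) takes police data "for a period 1 year prior to the recruitment date and for 3 months after completion of the intervention for all CYP". Protocol Table 2 says "Every CYP will have a 3-month follow-up period after completion of the intervention". The protocol's Primary outcome section gives the post-programme period as "3 months following the end of the interventions for each CYP".

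Programme length depends on the arm. In the SAP Introduction, "The RM intervention consists of 12 weeks of support comprised of three components", while for the RC sessions "they can all take place during a week or at most over four weeks".

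The headline estimate is an unadjusted intention-to-treat (ITT) regression with an arm indicator only. The SAP (Missing data; Compliance) keeps young people who disengage in that analysis.

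The wording is not uniform. The summary tables at the front of both documents, and the SAP Design overview, tie the three months to the end of delivery rather than to individual completion. The protocol Timeline also uses the end of delivery as a trial-level date, late February or early March 2025. The baseline year has three anchors: recruitment (SAP, Primary outcome analysis), the intervention ("for events 1 year prior to the intervention" in Protocol Table 2, and likewise in the SAP Design overview) and referral (the SAP covariate list).

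**The concern.** Completion happens after randomisation, and its timing is set largely by the arm. A window that opens at completion therefore opens 8 to 11 weeks later for RM than for RC. Contacts during RM's 12 weeks are not counted, while 8 to 11 of RC's 13 counted weeks fall in that same span.

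Participants enter after a violent offence or violent behaviour has come to notice, so a contact rate that changes with time since referral is plausible. If it does change, the arms differ even when neither programme works. The SAP argues that randomisation protects against biases in police recording. That does not cover this problem: randomisation balances who is in each arm, not when each arm is observed.

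Separately, someone who never completes has no completion date, so the primary outcome has no defined window for part of the ITT set.

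**Working it through.** **Inputs.** Window: 3 months, taken as 13 weeks. RM length: 12 weeks. RC length: c = 1 to 4 weeks (SAP Introduction). Assumption: programme start is close to randomisation.

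**The plan's own figures.** Neither document quantifies a window effect. The sample size does reproduce: for d = 0.3, two-sided alpha 0.05 and 80% power, 2 × (1.960 + 0.842)² / 0.3² = 174.4 per arm. The t-test version gives 175.4, so 176 per arm and 352 in total. The yardstick for the ratios below is the SAP's target incidence rate ratio of 1.22, or 1/1.22 = 0.82 as a reduction.

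**Step 1: where the windows fall.**
- RM: weeks 12 to 12 + 13 = 25.
- RC lasting 1 week: weeks 1 to 14; overlap with RM 14 − 12 = 2 weeks.
- RC lasting 4 weeks: weeks 4 to 17; overlap 17 − 12 = 5 weeks.

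**Step 2: ratio with no treatment effect.** Null ratio = (integral of the contact rate over weeks 12-25) / (integral over weeks c to c + 13). If the rate halves every h weeks, the common 13-week factor cancels and the ratio is 2^(−(12 − c)/h), that is 2^(−11/h) for c = 1 and 2^(−8/h) for c = 4. For the floor cases the rate is taken as proportional to 0.5 + 0.5 × 2^(−t/h), integrated the same way. All rate paths are assumptions.

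| Assumed contact rate | RC 1 week | RC 4 weeks |
|---|---|---|
| Flat | 1.00 | 1.00 |
| Halves every 104 weeks | 0.93 | 0.95 |
| Halves every 52 weeks | 0.86 | 0.90 |
| Halves every 26 weeks | 0.75 | 0.81 |
| Falls to a floor at half the starting rate, h = 52 | 0.94 | 0.95 |
| Falls to the same floor, h = 26 | 0.89 | 0.92 |
| Doubles every 52 weeks | 1.16 | 1.11 |

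**Step 3: effect on the test.** Take Poisson variance, an RC mean of 1.8 (the pilot control mean in the SAP's power footnote) and 176 per arm. The standard error of the log ratio R is √((1/1.8 + 1/(1.8R))/176). For R = 0.864 this is 0.083, and ln R = −0.146, so the chance of a significant result with no treatment effect is about 43%. For R = 0.899 it is about 26%. Overdispersion would lower these percentages but would not move the ratio.

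**Step 4: does a common window fit the timeline?** The protocol Timeline gives "CYP consented into the study until 30 November 2024" and "GMP data collection undertaken by: 6 June 2025". From 30 November 2024, 26 weeks (182 days) ends on 31 May 2025, six days before 6 June. A 25-week window (175 days) ends on 24 May, 13 days before. With the same window in both arms, the null ratio is 1.00 under any rate path.

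**The case against.** The strongest defence is that the SAP asks about post-treatment contact, and a window opening at the end of treatment follows from that question. Both windows are also equal in length. If the contact rate is flat over the first 25 weeks, the null ratio is exactly 1.00. The outcome includes contacts as a victim and missing-person episodes, which need not decline after the index incident. All of this stands: the existence, direction and size of a bias are not established by the documents. It does not remove the problem, because nothing in either document supports a constant rate, and the protocol's own research question is the broader one of impact on contact with the police.

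A second defence is that the front tables can be read as setting one calendar end date for everyone, which would not by itself separate the arms. Protocol Table 2, the protocol's Primary outcome section and the SAP analysis section point the other way. The inconsistency is a further reason to fix the definition.

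A reader might also infer something stronger: that contacts are counted from recruitment to three months after completion, giving RM about 25 weeks at risk against 14-17 for RC and a spurious ratio of 25/17 = 1.47 to 25/14 = 1.79. That would need counting from recruitment and no exposure offset. The text makes this unlikely. It speaks of contact after treatment and of three months from completion. The SAP's negative binomial density also carries an exposure period, although the two regression equations and the Poisson mean omit it.

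**Conclusion.** The documents establish that the arms are counted over different periods after randomisation, with 2-5 weeks in common, that the headline model does not correct for this, and that the window is undefined for non-completers. The headline ratio is therefore biased unless the contact rate is constant over about 25 weeks.

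It would go too far to say that the ratio is certainly biased, or biased in RM's favour. A falling rate favours RM, a rising rate favours RC, and a flat rate favours neither. Across the illustrated changing paths the null ratio runs from 0.75 to 1.16. Only the steepest decline shown reaches the size of the SAP's target (0.82 as a reduction), and the floor cases stay within 0.89-0.95. These figures rest on the assumed paths and on programmes starting close to randomisation. The gap for non-completers holds whatever the rate path.

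**What to change.** - **Primary window.** Count contacts over one fixed period from the randomisation date, identical in both arms and regardless of completion. Either 25 or 26 weeks covers 12 weeks of RM plus three months. Use 25 if randomisation can lag consent by more than six days; baseline questionnaires come between the two (Protocol Table 1).
- **Baseline.** Anchor the 12-month baseline count on the same date.
- **Post-treatment question.** Pre-specify contacts from week 13 to the end of the window, in both arms, as a secondary analysis.
- **Extract.** Specify that the police data cover the whole period from randomisation and are not drawn before the last participant's window closes.
- **Wording.** Make the front tables, Protocol Table 2, the protocol's Primary outcome section and the SAP agree.

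The cost is revised wording and extraction dates, with no follow-up beyond the planned data collection date. Two cautions apply. The extract as now described may omit the delivery period and later RC weeks, so the request must be widened before the data are pulled; with 26 weeks the margin is only six days. The primary count will also include contacts during delivery, a change of estimand that the authors must agree and state.
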